## Methods

The study was characterized as a randomized, double-blind, Sham-controlled trial and followed CONSORT guidelines. All procedures were approved by the Research Ethics Committee of the Federal University of São Carlos (CAAE 62842522.2.0000.5504) and registered at ClinicalTrials.gov (NCT05989815). All participants were informed about the study's objectives and signed an informed consent form.

## Sample Characterization

### Criteria for Eligibility

Male individuals between 18 and 35 years of age, practicing professional soccer and undergoing training at least 5 times per week, were selected. Individuals with any impediment to physical activity or dysfunctions affecting the neuromuscular system were excluded. Data collection took place at the Desportivo Brasil Football Club in Porto Feliz, SP. The sample consisted of team members, with a set number of 30 athletes established for the sample.

## Training Routine Description

The athletes underwent daily training sessions throughout the week, following the club's training routine as described on Table 1.

**Table 1** – Weekly Training Routine

| Period           | Monday                                                                       | Tuesday                                                                                    | Wednesday                                                                         | Thursday                                  | Friday                                     | Saturday                                |
|------------------|------------------------------------------------------------------------------|--------------------------------------------------------------------------------------------|-----------------------------------------------------------------------------------|-------------------------------------------|--------------------------------------------|-----------------------------------------|
| Morning   | Rest/Downtime                                                                | Gym
(strength
training
– 30
min) +
Field
(aerobic
activity
60 min) | Gym (strength
training – 30
min) + Field
(aerobic
activity 90
min) | Gym
(strength
training –
30 min) | Field (aerobic
activity 45 - 60
min) | Training
game or
Official
Game |
| Afternoon | Gym (strength
training 30
min) + Field
(aerobic
activity 60 min) | Field
(aerobic
activity 60 min)                                                      | Rest/Downtime                                                                     | Field
(aerobic
activity 60 min)     | Downtime/Rest                              | Rest                                    |

|  |                     |
|--|---------------------|
|  | activity 45
min) |
|--|---------------------|

## Randomization and Allocation Concealment

The randomization was conducted using the website randomization.com, and the participants were allocated into three groups of ten individuals each. To ensure allocation concealment, sealed opaque envelopes were used, containing the randomly assigned interventions: PBM-post, PBM-pre, and PBM-Sham. Only one researcher (therapist 1) was involved in this process, being responsible for applying PBM to all participants. This researcher was blinded to the other assessments in the study, which were conducted by therapist 2. Participants were unaware of which intervention was applied during the study.

## Study Design

[figure not shown]
The selected individuals were allocated into 3 equal groups and randomized according to the type of intervention:

- **PBM Post-Exercise Group (PBM-Post):** Submitted to the protocol of muscle damage induction and Sham photobiomodulation pre-exercise, followed by active post-exercise photobiomodulation.
- **PBM Pre-Exercise Group (PBM-Pre):** Submitted to the protocol of muscle damage induction and active pre-exercise photobiomodulation, followed by Sham post-exercise photobiomodulation.
- **PBM Sham Group (PBM-Sham):** Submitted to the protocol of muscle damage induction and Sham photobiomodulation both pre and post-exercise.

On the 1st day, all individuals were assessed using the one-repetition maximum (1RM) test to measure the loads for the muscle damage induction protocol. On the 2nd day (24 hours after the 1RM test), all groups underwent initial assessment tests (T1), which included: a) Anamnesis through a questionnaire. b) Measurement of blood levels of creatine phosphokinase (CK) using the Roche Hitachi 917 biochemical analyzer. c) Delayed onset muscle soreness (DOMS) using the numeric rating scale (NRS) and the pain location area using the pain map (mapDOMS). d) Muscle performance tests on a jump platform (Squat Jump test – SJ and Counter Movement Jump - CMJ). e) Dynamometry of the dominant knee extensor muscles with the Manual Muscle Test equipment (Lafayette Instrument).

Also on the 2nd day, the groups were irradiated with whole-body PBM (Sham or active) followed by the muscle damage induction protocol. Sequentially, participants underwent vertical jump and dynamometry tests (T2). Ten minutes after T2, participants were irradiated with active PBM or Sham according to their allocation in the groups.

Finally, on the 3rd, 4th, and 5th days, participants were reassessed (T3) for CK, DOMS, SJ/CMJ, and Dynamometry at 24h, 48h, and 72h after the muscle damage induction protocol. The study design is summarized in Figure 1.

**Figure 1.** Study Flowchart

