### 3.7 Sample Size Calculation

The sample size ( $n=30$ ) was calculated a priori using GPower 3.1 software. It considered 3 groups, 4 assessment time points (immediately after the muscle damage induction protocol, and at 24h, 48h, and 72h after), a minimum effect size of 0.25, a test power of 80%, and a significance level of 5%, for comparisons through two-way repeated measures analysis of variance.

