## Data Analysis

Data analysis was conducted by a researcher blinded to participant group allocation. The primary outcome of the study was considered the muscle damage measured by CK levels.

The data were descriptively analyzed using mean and standard deviation. The independent variables were the experimental conditions (Sham, PBM-pre, and PBM-post) and assessment times pre, 24h, 48h, 72h after the muscle damage induction protocol. Normality and homoscedasticity assumptions were tested beforehand using the Shapiro-Wilk W Test and Levene test, respectively. The dependent variables included CK, DOMS, height of jumps in Squat Jump (SJ) and Counter Movement Jump (CMJ), and isometric manual dynamometry of the femoral quadriceps (kgf).

Two-way repeated measures analysis of variance (ANOVA) was conducted (considering pre, 24h, 48h, and 72h after the muscle damage induction protocol) followed by Tukey's post hoc test when the data showed normal distribution and variance homogeneity. In cases where the data did not present normal distribution, a logarithmic transformation (log10) was adopted, and normality and variance homogeneity were verified again for parametric tests. If the data did not meet the assumptions of normality and variance homogeneity, non-parametric tests such as Friedman's ANOVA (intragroup analyses) and Kruskal-Wallis (intergroup analyses) were employed. The significance level was set at 5%. Statistical analysis was performed using a statistical software (SPSS Statistics for Windows version 20.0, IBM, Chicago, IL, United States).

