### **Counter Movement Jump (CMJ)**

The repeated measures ANOVA did not reveal a moment interaction ( $F_{2,27} = 0.166$ ) and moment versus treatment interaction ( $F_{2,27} = 0.127$ ). As there was no significant interaction, the Tukey post hoc analysis was not conducted. The means and standard deviations for the Counter Movement Jump (CMJ) are presented in Table 9.

**Table 9.** Mean values ( $\pm$  standard deviation) of Counter Movement Jump (CMJ) in centimeters for the Sham, PBM-pre, and PBM-post groups at pre, immediately after, 24h, 48h, and 72h after the muscle damage induction protocol:

| Groups          | CMJ pre             | CMJ post            | CMJ 24h             | CMJ 48h             | CMJ 72h             |
|-----------------|---------------------|---------------------|---------------------|---------------------|---------------------|
| Sham     | 40.86 ( $\pm$ 4.68) | 40.49 ( $\pm$ 4.16) | 39.94 ( $\pm$ 3.64) | 41.11 ( $\pm$ 4.16) | 40.35 ( $\pm$ 4.76) |
| PBM-pre  | 41.17 ( $\pm$ 7.09) | 42.51 ( $\pm$ 7.66) | 40.93 ( $\pm$ 5.82) | 40.21 ( $\pm$ 6.22) | 42.98 ( $\pm$ 6.86) |
| PBM-post | 38.29 ( $\pm$ 3.55) | 39.57 ( $\pm$ 3.89) | 39.30 ( $\pm$ 4.59) | 39.64 ( $\pm$ 4.70) | 39.99 ( $\pm$ 4.60) |

**Abbreviations:** PBM (photobiomodulation); CMJ (Counter Movement Jump).

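### At T2 the Sham and PBM-post arms have had the same exposure; the fixed three-arm analysis of the jump and force endpoints is valid but leaves precision unused

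*Combined protocol and SAP*

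**What the plan says.** Randomization and Allocation Concealment: "the participants were allocated into three groups of ten individuals each".

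Study Design gives the order of events on day 2: T1 tests, first irradiation, induction exercise, T2 jump and force tests, second irradiation. On the second irradiation it says: "Ten minutes after T2, participants were irradiated with active PBM or Sham according to their allocation in the groups". The PBM-post arm receives "Sham photobiomodulation pre-exercise, followed by active post-exercise photobiomodulation". The Sham arm is described as "Submitted to the protocol of muscle damage induction and Sham photobiomodulation both pre and post-exercise".

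Data Analysis defines one grouping for all endpoints and times: "The independent variables were the experimental conditions (Sham, PBM-pre, and PBM-post) and assessment times". Neither it nor the Statistical Analysis Plan (Summary) provides for the two arms that are alike at T2, or for T2 as a pre-treatment measurement in PBM-post.

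The documents differ on whether T2 is analysed. The ANOVA in Data Analysis lists pre, 24 h, 48 h and 72 h. Section 3.7 counts T2 and leaves out baseline. Tables 8–10 print five times by three arms; Table 9, for example, gives means "at pre, immediately after, 24h, 48h, and 72h after the muscle damage induction protocol".

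**The concern.** A comparison at a given time should reflect what each athlete has received by then. At T2 only PBM-pre has had active light, so the contrast available is active (n=10) against sham (n=20). A fixed three-arm factor uses 10 of those 20 controls in PBM-pre versus Sham.

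For PBM-post versus Sham, T2 comes before the treatments diverge. It is a second pre-treatment measurement and could serve as a covariate for the later visits. In a five-time ANOVA it is an outcome level instead.

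What is at stake is precision. The abstract concludes that neither timing of light improved or worsened performance, and that null statement rests on 10 athletes per arm.

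**Working it through.** **Plan's own figure.** Section 3.7 gives N=30 from 3 groups, 4 times, effect size f=0.25, power 80% and alpha 5%. For the group-by-time interaction, taking correlation 0.5 and no sphericity correction (both assumed), the noncentrality is 30×4×0.25²/(1−0.5) = 15 with 6 and 81 df. Power is 0.809 at N=30 and 0.792 at N=29, so 30 reproduces. The calculation does not distinguish T2 from later visits.

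**Did T2 enter the reported performance models?** In one repeated-measures ANOVA the time test and the interaction test share an error mean square (MSE). I read the values printed after F as p-values, took the mean squares from the means in Tables 8–10, and solved for the MSE from each test.

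| Endpoint | Five times, 108 error df: time / interaction | Four times, 81 error df: time / interaction |
|---|---|---|
| Squat jump | 4.11 / 4.10 | 3.79 / 5.84 |
| Countermovement jump | 3.98 / 3.97 | 4.09 / 4.33 |
| Force | 36.4 / 36.6 | 43.3 / 27.2 |

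The five-time solutions agree for all three endpoints. The four-time solutions clearly disagree for squat jump and force. This is good evidence that T2 was included. It remains an inference, because the printed degrees of freedom (2, 27) fit neither model.

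**PBM-pre against control at T2.** The SE is proportional to √(1/10+1/10) = 0.447 with Sham alone and √(1/10+1/20) = 0.387 with the pooled 20. The ratio is 0.866, so the SE is 13.4% smaller, assuming equal variance in all arms.

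For change from T1 to T2, SE = √(2×MSE×0.20) or √(2×MSE×0.15):

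| Endpoint | Change: Sham, PBM-pre, PBM-post | PBM-pre − Sham (SE) | PBM-pre − pooled 20 (SE) |
|---|---|---|---|
| Squat jump, cm | −0.15, 0.46, 1.35 | 0.61 (1.28) | −0.14 (1.11) |
| Countermovement jump, cm | −0.37, 1.34, 1.28 | 1.71 (1.26) | 0.885 (1.09) |
| Force, kgf | 3.42, 4.15, −0.86 | 0.73 (3.82) | 2.87 (3.31) |

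Every estimate is less than 1.4 SE from zero.

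**PBM-post against Sham at one later visit.** Let ρ be the correlation between any two times, with equal variances. The ANCOVA residual variance is 1−ρ² with T1 alone and 1−2ρ²/(1+ρ) with T1 and T2. The SE ratio simplifies to √(1+2ρ)/(1+ρ).

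The documents print no correlation. One is implied by ρ = 1 − MSE/(mean squared SD in Tables 8–10):

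- Squat jump: 1 − 4.10/28.08 = 0.85; SE 11.2% smaller.
- Countermovement jump: 1 − 3.98/27.54 = 0.86; SE 11.3% smaller.
- Force: 1 − 36.5/98.95 = 0.63; SE 7.8% smaller.
- For comparison, ρ = 0.5: √2/1.5 = 0.943; SE 5.7% smaller.

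These are large-sample ratios. Estimating a second slope from 20 athletes takes back part of the gain.

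**The case against.** The strongest objection is that nothing is wrong with the three-arm test. The arms are randomized, and a time at which two of them have no true difference neither biases the F test nor inflates its type I error. This stands: the point concerns efficiency.

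Three stronger readings are tempting, and the documents do not support them.

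- **A chance gap at T2 was read as a treatment effect.** PBM-post minus Sham in T1-to-T2 change is +1.50 cm, +1.65 cm and −4.28 kgf with identical exposure. On the SEs above these give t = 1.17, 1.31 and −1.12, which is ordinary chance variation. No T2 gap is interpreted anywhere: post hoc tests were not run for the jumps and found nothing for force.
- **The PBM-post value at T2 distorts PBM-pre versus Sham.** It does not enter that difference. The moves in the right-hand columns of the table result from pooling and do not show a fault in the randomized contrast.
- **Both contrasts lose precision throughout.** The pooling gain applies at T2 only, because by 24 h PBM-post has had active light. PBM-pre versus Sham at 24–72 h loses nothing. The gain for PBM-post comes from a separate device.

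Two further objections stand in part. T2 follows eight exercises of 3×10 repetitions, so it is a fatigued state and may predict later visits differently from T1; the Sham force SD is 14.98 kgf at T1 and 10.38 at T2, which strains the equal-variance assumption. And redefining comparators after the arm means are known is post hoc.

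**Conclusion.** The point holds as a modest, nearly free gain in precision for secondary endpoints.

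- At T2 only, comparing PBM-pre with all 20 sham-exposed athletes makes the SE 13% smaller. This assumes equal arm variances.
- At 24–72 h, adding T2 as a covariate for PBM-post versus Sham makes the SE about 8–11% smaller, assuming equal variances and correlations across times at the implied 0.63–0.86. At 0.5 it is about 6%. The true gain may be smaller because of fatigue at T2 and the small sample.

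That T2 was an outcome level in the reported models is inferred from the p-values. If it was left out, both gains are still unused.

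A reader might infer that the reported performance findings are biased or would be overturned. Neither follows. Creatine kinase (primary) and soreness are not measured at T2, so the claims about them are untouched.

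**What to change.** In the Statistical Analysis Plan (Summary) and Data Analysis, add for squat jump, countermovement jump and force:

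- (a) At T2: PBM-pre (n=10) against Sham plus PBM-post (n=20), adjusted for T1.
- (b) At 24, 48 and 72 h: PBM-post against Sham, adjusted for T1 and T2; PBM-pre against Sham, adjusted for T1 only, because T2 follows active light in PBM-pre.

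In these analyses do not treat T2 as a post-treatment level for PBM-post. Report estimates with 95% confidence intervals beside the three-arm ANOVA, and label them post hoc because the arm means are known. State at the same time whether T2 belongs to the performance ANOVA, so that section 3.7, Data Analysis and Tables 8–10 agree; adding T2 to the list of times would not by itself say who is compared with whom there.

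Cost: a few lines of text and a re-run on data already collected, complete for all 30 athletes. The downside is that covariates differ between contrasts, which needs a sentence of explanation.

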### ***Squat Jump (SJ)***

A repeated measures ANOVA did not reveal a moment interaction ( $F_{2,27} = 0.177$ ) and moment versus treatment interaction ( $F_{2,27} = 0.834$ ). As there was no significant interaction,

Tukey's post hoc analysis was not conducted. The means and standard deviation for SJ are presented in Table 8.

**Table 8.** Mean values ( $\pm$  standard deviation) of SJ (cm) for the Sham, PBM-pre, and PBM-post groups at pre, immediately after, 24h, 48h, and 72h after the muscle damage induction protocol:

| Groups          | SJ pre              | SJ post             | SJ 24h              | SJ 48h              | SJ 72h              |
|-----------------|---------------------|---------------------|---------------------|---------------------|---------------------|
| Sham     | 39.80 ( $\pm$ 4.60) | 39.65 ( $\pm$ 4.20) | 38.56 ( $\pm$ 4.09) | 40.10 ( $\pm$ 3.89) | 39.12 ( $\pm$ 4.13) |
| PBM-pre  | 39.96 ( $\pm$ 7.40) | 40.42 ( $\pm$ 7.54) | 38.91 ( $\pm$ 5.45) | 39.63 ( $\pm$ 6.94) | 40.32 ( $\pm$ 7.08) |
| PBM-post | 37.04 ( $\pm$ 3.74) | 38.39 ( $\pm$ 4.68) | 37.38 ( $\pm$ 5.22) | 38.18 ( $\pm$ 4.07) | 38.20 ( $\pm$ 3.77) |

**Abbreviations:** PBM (photobiomodulation); SJ (Squat Jump).

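### T2 jumps and force are a second pre-treatment measurement for PBM-post versus Sham, but the plan gives T2 no role, so these secondary contrasts are less precise than the collected data allow

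*Combined protocol and SAP*

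**What the plan says.** Study Design sets the order of day 2: T1 tests, first irradiation, damage protocol, T2 (jumps and dynamometry only), then the second irradiation: "Ten minutes after T2, participants were irradiated with active PBM or Sham according to their allocation in the groups". The arms are:

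- PBM-post: "Sham photobiomodulation pre-exercise, followed by active post-exercise photobiomodulation"
- PBM-pre: "active pre-exercise photobiomodulation, followed by Sham post-exercise photobiomodulation"
- Sham: "Submitted to the protocol of muscle damage induction and Sham photobiomodulation both pre and post-exercise"

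Data Analysis specifies a two-way repeated-measures ANOVA "considering pre, 24h, 48h, and 72h after the muscle damage induction protocol". T2 is not in that list, and neither this section nor the Statistical Analysis Plan summary names a covariate. Section 3.7 (Sample Size Calculation) uses a different set of four times, with T2 in and T1 out. Tables 8 to 10 show all five times: "pre, immediately after, 24h, 48h, and 72h after the muscle damage induction protocol". CK, the primary endpoint, and DOMS are not measured at T2. The Abstract concludes that neither regimen changed performance in either direction.

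**The concern.** Through T2, PBM-post and Sham athletes have had the same sham light, the same exercise and the same tests. For that pair, T2 is the last measurement before treatment differs, and the only one that reflects each athlete's immediate response to the exercise. An analysis that ignores it, or enters it as another outcome time, does not use it to explain variation at 24, 48 and 72 h. With ten athletes per arm and a conclusion of no performance effect, the width of the intervals is what matters, so avoidable noise has a cost. The mismatch between the time lists in Section 3.7 and Data Analysis is a separate fault. Repairing it by adding T2 as a fifth outcome level would still leave T2 unused as pre-treatment information.

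**Working it through.** **1. The plan's own figure.** Section 3.7 gives N = 30 for 3 groups, 4 times, f = 0.25, power 80%, alpha 5%. For the group-by-time interaction with correlation 0.5 (assumed; none is stated), lambda = 0.0625 × 30 × 4 / 0.5 = 15 on 6 and 81 df, and power is 0.809. N = 30 therefore reproduces, for an omnibus test with no covariate.

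**2. Light received by T2.**

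| Arm | Before T2 | After T2 | Status of T2 |
|---|---|---|---|
| Sham | sham | sham | pre-treatment |
| PBM-post | sham | active | pre-treatment |
| PBM-pre | active | sham | post-treatment |

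**3. Did T2 enter the reported ANOVAs?** The results do not say. The values printed as F(2,27) are read here as p-values: time 0.177, 0.166, 0.034 and interaction 0.834, 0.127, 0.486 for SJ, CMJ and force. From the cell means in Tables 8 to 10, each p-value implies an error mean square, MSE = effect mean square / F quantile. SJ with five levels:

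- Time: 26.48/4 = 6.62; F(4,108) at p = 0.177 is 1.61; MSE 4.11.
- Interaction: 17.27/8 = 2.16; F(8,108) at p = 0.834 is 0.527; MSE 4.10.

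The two values should agree if the set of times is right (time / interaction):

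| Times used | SJ | CMJ | Force |
|---|---|---|---|
| All five | 4.11 / 4.10 | 3.98 / 3.97 | 36.4 / 36.6 |
| T1, 24, 48, 72 h | 3.79 / 5.84 | 4.09 / 4.33 | 43.3 / 27.2 |
| T2, 24, 48, 72 h | 5.15 / 2.90 | 4.00 / 3.84 | 19.3 / 43.2 |

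Only five levels fit SJ and force. CMJ points the same way but is less decisive.

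**4. Within-athlete correlation.** Under compound symmetry r = 1 − MSE / mean cell variance V:

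- SJ: 1 − 4.10/28.08 = 0.854
- CMJ: 1 − 3.98/27.54 = 0.856
- Force: 1 − 36.5/98.95 = 0.631

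**5. Precision.** Residual variance as a share of V is 1 − r² with T1 alone and 1 − 2r²/(1+r) with T1 and T2.

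- Jumps (SJ shown): 0.271 to 0.213, ratio 0.79, so 21% less variance; √0.79 = 0.89, so 11% narrower.
- Force: 0.602 to 0.512, ratio 0.85, so 15% less variance; √0.85 = 0.92, so 8% narrower.

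These ignore the cost of a second covariate with 20 athletes. Allowing for it by the expected inflation (17/15)/(17/16) = 1.067 and t quantiles 2.120/2.110 gives √(0.788 × 1.067) × 1.005 = 0.92 for jumps and √(0.850 × 1.067) × 1.005 = 0.96 for force, about 8% and 4% narrower. For r from 0.5 to 0.9 the variance reduction before this cost is 11% to 22%.

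**6. Estimates, PBM-post minus Sham.** Let d be the difference in means at each time. T1 only: d − r·d(T1). T1 and T2: d − [r/(1+r)]·[d(T1) + d(T2)], with r/(1+r) = 0.461, 0.461 and 0.387.

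| | d at T1, T2, 24, 48, 72 h | T1 only, 24/48/72 h | T1 and T2, 24/48/72 h |
|---|---|---|---|
| SJ (cm) | −2.76, −1.26, −1.18, −1.92, −0.92 | +1.18/+0.44/+1.44 | +0.67/−0.07/+0.93 |
| CMJ (cm) | −2.57, −0.92, −0.64, −1.47, −0.36 | +1.56/+0.73/+1.84 | +0.97/+0.14/+1.25 |
| Force (kgf) | +9.12, +4.84, +3.61, +7.92, +8.47 | −2.15/+2.16/+2.71 | −1.79/+2.52/+3.07 |

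For example, SJ at 72 h: −0.92 + 0.854 × 2.76 = +1.44, and −0.92 + 0.461 × 4.02 = +0.93. The T1-only standard error, √{V(1 − r²)[2/10 + d(T1)²/(18V)]}, is about 1.3 cm for jumps and 3.8 kgf for force, so every shift is well under one standard error.

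**7. Acute contrast at T2.** PBM-pre against Sham alone has variance proportional to 1/10 + 1/10 = 0.20. Against Sham and PBM-post pooled it is 1/10 + 1/20 = 0.15, which is 25% less if the arms share a variance. For the jumps PBM-pre has the larger SDs (SJ at T2: 7.54 against 4.20 and 4.68), so the gain there would be smaller.

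**The case against.** The strongest reply is that nothing here is an error. T1 precedes all irradiation in a randomised trial, so it is a valid common baseline. Divergence between two identically treated arms from T1 to T2 is chance: at an assumed correlation of 0.7 its p-values are about 0.34, 0.26 and 0.30 for SJ, CMJ and force, and the ANOVA error term already allows for such variation. All of this stands.

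A reader might infer that pre-treatment differences are being read as a response to PBM. The documents do not support that: the interactions are non-significant and no performance effect is claimed.

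A reader might also compare raw changes from T1 with raw changes from T2 (at 72 h, SJ +1.84 against +0.34 cm and force −0.65 against +3.63 kgf) and infer that most of the jump difference preceded treatment and that the force result changes sign. The plan names no change-score endpoint, and neither score is proposed here. The force reversal comes mainly from the T1 imbalance (50.41 against 59.53 kgf), which T1 adjustment alone handles: force keeps its sign at every time when T2 is added.

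It is also fair to say that T2 cannot enter one three-arm model as a common covariate. It follows active light in PBM-pre, and adjusting for it there could remove part of that arm's effect. An immediate post-exercise value may also correlate less with later values than assumed here.

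**Conclusion.** The point holds as lost precision on secondary endpoints. For PBM-post versus Sham, T2 is pre-treatment information that the plan does not use as such. The gain from using it is about 21% (jumps) and 15% (force) in residual variance, with intervals at most 11% and 8% narrower and somewhat less after the extra degree of freedom. Pooling reduces the T2 contrast variance by 25% under equal variances. These figures rest on compound symmetry, on reading the printed values as p-values, and on the inferred correlations; the documents report no correlations. The estimates move modestly and do not overturn the performance conclusion. SJ at 48 h passes from +0.44 to −0.07 cm, which is negligible against its standard error. CK, DOMS and the claims based on them are untouched.

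**What to change.** For SJ, CMJ and force, state in Data Analysis:

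- PBM-post versus Sham at 24, 48 and 72 h: ANCOVA or a mixed model adjusted for T1 and T2.
- PBM-pre versus Sham at the same times: adjusted for T1 only.
- Acute contrast at T2: PBM-pre (n = 10) against Sham and PBM-post pooled (n = 20), adjusted for T1, allowing unequal variances if the SDs differ.

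Report estimates with confidence intervals, since the conclusion is one of no effect, and label the re-analysis post hoc because results are already known. Also say explicitly which times entered the reported ANOVAs, and reconcile the lists in Section 3.7 and Data Analysis.

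The cost is SAP wording and a re-run on data already collected, complete for all 30 athletes. The downsides are one degree of freedom, different covariate sets for the two active arms, and separate pairwise models that should be presented as secondary estimates.
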